## Management and Safety Surveillance for Non-Cutaneous Squamous Cell Carcinoma:

- A thorough head and neck examination to monitor for non-cutaneous SCC, consisting of at least a visual inspection of the oral mucosa and lymph node palpation, must be performed by the treating physician or other qualified physician at screening for all patients enrolled. The most current examination from the antecedent protocol may be utilized as the screening examination for the extension (rollover) protocol if it was conducted within 30 days prior to the first dose of vemurafenib. Subsequent head and neck examinations will be performed as outlined in Section 4.5.1.10.
- Chest CT scans must be performed at baseline, within 30 days before the start of study treatment and then every 6 months (with a window of  $\pm 21$  days) after initiation of treatment until death, withdrawal of consent, *or* loss to follow-up, whichever occurs first. Available routine chest CT scans from previous assessments may be used, as outlined in Section 4.5.1.10.
- Additionally, all patients are required to undergo examination (visual and digital) of the anus and anal canal by the treating physician or his/her designee at baseline and at the end of the study (end of treatment visit). The most current examination from the antecedent protocol may be used, as outlined in Section 4.5.1.10.
- Female patients must have a pelvic examination (including evaluation of the uterine cervix by Pap smear) at baseline and at the end of the study (end of treatment visit), performed by a gynecologist or designee. The most current examination from the antecedent protocol may be used, as outlined in Section 4.5.1.10.
- An unscheduled examination may be performed during treatment for the investigation of any new lesion or symptom suspected to be SCC (head and neck, anus, pelvic for female patients only, chest CT).

## New Primary Invasive Malignancies

All new primary invasive malignancies will be reported until *28 days* after treatment completion, withdrawal of consent, loss to follow-up, or death, whichever occurs earliest.

If a patient develops a new primary invasive malignancy during or up to *28 days* after study treatment completion, this event must be reported to the Sponsor as a serious adverse event, whether it is deemed related or unrelated to study drug. Thereafter, only new primary malignancies thought to be related to study treatment will be reported as serious adverse events.

Any identified lesion suspected to be a new primary malignancy (including cuSCC, non-cutaneous SCC, and/or new primary melanoma) must be biopsied or excised and sent for pathological examination and should be treated according local institutional standard of care.

## **Hepatic Toxicity**

Cases of liver injury, including severe cases of liver injury, have been reported with vemurafenib use. These have been generally managed with interruption of treatment and dose reduction. All patients will undergo liver function testing at periodic intervals while on study treatment (see [Appendix 1](#)). Guidelines for interruption or dose reduction of vemurafenib in the setting of liver function abnormality are provided in Section [5.1.3](#).

See also the Vemurafenib IB for updated safety information.

## **Hematologic Toxicity**

Patients will have hematologic parameters monitored throughout the study. See the Vemurafenib IB for full details of potential hematologic adverse events reported in association with vemurafenib treatment.

## **Gastrointestinal Toxicity**

Gastrointestinal toxicities will be managed according to institutional guidelines/standard of care. During the study, patients are to receive maximal supportive care as clinically indicated. Any modification of study treatment for diarrhea must strictly follow the instructions in [Table 1](#).

## **Pancreatic Toxicity**

The Sponsor recommends that workup of any suspected case of pancreatitis should include serum amylase and lipase testing, in addition to other appropriate testing (e.g., CT abdomen).

## **Ocular Toxicity**

See the Vemurafenib IB for further details on the occurrence of anterior uveitis and a single case of retinal vein occlusion reported in association with vemurafenib treatment.

Examination of the eyes (inspection of conjunctivae and pupils) is part of the physical examination.

## **Cardiac Toxicity**

Patients with a baseline QTc >450 ms or a history of congenital long QT syndrome should not receive treatment with vemurafenib. Refer to the Vemurafenib IB for additional details.

The following recommendations have been developed to minimize the risk of cardiac toxicity in patients with metastatic melanoma treated with vemurafenib in this study:

- Avoid combination with other medications with known potential to lead to prolongation of the QTc interval, if possible (see [Appendix 4](#))
- ECG monitoring will occur at baseline and at specified intervals, as outlined in the Schedule of Assessments (see [Appendix 1](#)).

- If the QTc increases to > 500 ms, or if a change from baseline of  $\geq 60$  ms is observed during the study, vemurafenib treatment should be temporarily interrupted. Electrolytes (K, Mg, albumin, and Ca) should be monitored, and any electrolyte abnormalities, especially hypokalemia, should be corrected prior to re-institution of therapy. ECG should be monitored weekly until the QTc normalizes before therapy is reinstated at a reduced dose. Dose reduction should occur as described in [Table 1](#). A second sustained occurrence of QTc interval prolongation to > 500 ms, despite dose reduction, will require discontinuation of vemurafenib.
- Vemurafenib treatment should be permanently discontinued if the QTc increases to > 500 ms and changes from baseline exceed 60 ms.

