**Table 1 Dose Interruption/Modification Criteria for Vemurafenib; Regular Dose 960 mg BID**

Grade a	Recommended Dose Modification
Grade 1 or Grade 2 (tolerable)	Maintain vemurafenib at a dose of 960 mg BID
Grade 2 (intolerable) or Grade 3	
First appearance	Interrupt treatment until Grade 0–1. Resume dosing at 720 mg BID
Second appearance	Interrupt treatment until Grade 0–1. Resume dosing at 480 mg BID
Third appearance	Discontinue permanently
Grade 4	
First appearance	Discontinue permanently or interrupt vemurafenib treatment until Grade 0–1. Resume dosing at 480 mg BID
Second appearance	Discontinue permanently

BID=twice daily; NCI CTCAE=National Cancer Institute Common Terminology Criteria for Adverse Events.

a The intensity of clinical adverse events graded by the NCI CTCAE, Version 4.0.

Special consideration must be taken with any patient in the study who experiences an increase in QTc > 500 ms or change from baseline > 60 ms. If the QTc exceeds 500 ms or the change from baseline is > 60 ms on ECG, vemurafenib treatment should be temporarily interrupted. When the QTc decreases to < 500 ms, re-initiation of vemurafenib treatment may occur and the dose should be reduced by one dose level.

Permanent discontinuation of vemurafenib treatment is recommended if the QTc increase meets both criteria of > 500 ms and > 60 ms change from pretreatment.

Dose modifications or interruptions are not recommended for cuSCC or new primary melanoma adverse reactions (suspected lesion should be biopsied or resected and confirmed by pathology). Confirmed cuSCC or new primary melanoma should be completely resected and treated according local institutional standard of care.

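### Sections 5.1.2.3 and 5.1.3 give different QTc interruption, restart and stopping rules with no stated precedence, and the 5.1.3 restart value does not work for a patient interrupted only for a change from baseline

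*Combined protocol and SAP*

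**What the plan says.** Section 4.3.2.1 sends sites to Section 5.1 as a whole for interruption, dose modification and discontinuation. Two parts of Section 5.1 deal with QTc.

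**Section 5.1.2.3, Cardiac Toxicity.** These rules are introduced as recommendations for patients with metastatic melanoma.
- Interruption: on a QTc above 500 ms, or where a rise from baseline of ≥60 "ms is observed during the study, vemurafenib treatment should be temporarily interrupted".
- Restart: "any electrolyte abnormalities, especially hypokalemia, should be corrected prior to re-institution of therapy", and "ECG should be monitored weekly until the QTc normalizes before therapy is reinstated at a reduced dose". No number defines a normalized QTc. The size of the reduction is referred to Table 1.
- Repeat event: "A second sustained occurrence of QTc interval prolongation to > 500 ms, despite dose reduction, will require discontinuation of vemurafenib".
- Permanent stop: "Vemurafenib treatment should be permanently discontinued if the QTc increases to > 500 ms and changes from baseline exceed 60 ms".

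**Section 5.1.3, text under Table 1.** This is addressed to any patient in the study.
- Interruption: "If the QTc exceeds 500 ms or the change from baseline is > 60 ms on ECG", treatment is stopped temporarily.
- Restart: "When the QTc decreases to < 500 ms, re-initiation of vemurafenib treatment may occur and the dose should be reduced by one dose level". Electrolytes, weekly ECGs and the change from baseline are not mentioned.
- Permanent stop: only recommended, where the increase "meets both criteria of > 500 ms and > 60 ms change from pretreatment".
- Repeat event: the QTc text says nothing.

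Neither section says which governs.

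**The concern.** Section 5.1.3 has two interruption triggers, an absolute QTc and a change from baseline, but its restart condition addresses only the first. A site working from the text under Table 1 could restart the drug while the QTc is still more than 60 ms above baseline. Section 5.1.2.3 would hold it.

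The stake is patient safety at the sites, for four reasons found in the protocol:

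- Section 1.2.1.5 reports that mean QTc prolongation tracked mean vemurafenib concentration. Section 1.2.1.3 gives a median half-life of 57 hours (5th to 95th percentile 30 to 120), so an immediate restart allows little washout.
- From Cycle 18, Appendix 1 schedules ECGs every third cycle, that is every 3 × 28 = 84 days. Without the weekly ECGs of 5.1.2.3, further tracings are discretionary.
- Section 5.2.3 requires 24-hour reporting only for Grade 3 or 4 QTc prolongation. Section 1.2.1.5 labels an increment above 60 ms as Grade 2. If that label carries over, a non-serious change-only event does not reach the sponsor quickly.
- Under Section 5.1.3 an interruption longer than 28 days counts as permanent discontinuation, with limited exceptions. An undefined restart criterion can therefore decide whether a patient keeps access, which is the primary objective.

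**Working it through.** The plan has no figure to reproduce. The check applies both rules to the same patients. Let B be the reference QTc and Q the on-study QTc, in ms.

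**Triggers.** Section 5.1.2.3: Q > 500 or Q − B ≥ 60. Section 5.1.3: Q > 500 or Q − B > 60. They differ only when Q − B = 60 exactly and Q ≤ 500.

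**Restart after a change-only interruption.** Change-only means Q − B > 60 and Q ≤ 500. The 5.1.3 value, Q < 500, is then already met on the triggering ECG unless Q is exactly 500.

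| B | Q | Change | 5.1.2.3 | 5.1.3 | Q < 500 on the triggering ECG? |
|---|---|---|---|---|---|
| 400 | 460 | 60 | Interrupt | Continue | Not applicable |
| 400 | 470 | 70 | Interrupt | Interrupt | Yes |
| 430 | 495 | 65 | Interrupt | Interrupt | Yes |
| 445 | 503 | 58 | Interrupt | Interrupt | No; the rule works |
| 430 | 503 | 73 | Should stop permanently | Stop recommended | No |

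In the last row, a site that does not take up the 5.1.3 recommendation could restart at Q = 499, where the change is 499 − 430 = 69 ms, still above the trigger.

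**How general the restart defect is.** Take whole-millisecond values, B from 360 to 450 (450 being the baseline limit in 5.1.2.3) and Q from 360 to 560; the bounds 360 and 560 are assumptions. For each B there are 440 − B change-only values of Q. Summed over B = 360 to 439 this gives 80 × 81 / 2 = 3,240 combinations, of which 80 have Q = 500. The other 3,160 already meet Q < 500. These counts describe the rule, not how often patients fall there.

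If the permanent stop is always applied, a temporary stop for Q > 500 alone needs Q − B ≤ 60, so B is 441 to 450 and Q is 501 to 510. At B ≤ 440 every temporary stop is then change-only. This bound fails if the 5.1.3 recommendation is treated as optional.

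**Reference ECG.** Section 4.5.2.1 and Appendix 1 allow the screening ECG to come from the antecedent study if taken within 14 days before the first dose. Section 3.1.1 limits the dosing gap to 15 days. The tracing may therefore be on drug or soon after it. As an illustration, suppose the pre-vemurafenib QTc was 400 ms and the screening ECG is shifted by 17.7 ms, the highest upper confidence bound for mean prolongation in Section 1.2.1.5. An on-study QTc of 470 ms is then 70 ms above the pre-vemurafenib value but 470 − 417.7 = 52.3 ms above screening. The first reference interrupts treatment; the second does not.

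**Frequency.** From the Phase II figures in Section 1.2.1.5 (n = 132), with exact binomial 95% intervals:
- increment > 60 ms: 1/132 = 0.8% (0.02% to 4.1%);
- QTc > 500 ms: 2/132 = 1.5% (0.2% to 5.4%);
- either: at most 3/132 = 2.3% (0.5% to 6.5%), or 2/132 if the groups overlap.

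A change of exactly 60 ms is not reported.

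**The case against.** The strongest reply is that a fall to below 500 ms naturally describes a QTc that had been at or above 500. The 400-to-470 ms patient is then outside the 5.1.3 restart sentence and falls under 5.1.2.3, which does supply a rule. The 5.1.3 wording is also permissive, so a site that follows 5.1.2.3 satisfies both sections. This stands as mitigation, and it rules out saying that the protocol has no restart rule for such a patient or requires an unsafe restart. It does not remove the inconsistency: on that reading 5.1.3 has no restart rule for one of its own two triggers, and the rule in 5.1.2.3 rests on an undefined term in text addressed to metastatic melanoma, although Section 3.4.2 admits other tumour types.

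Three stronger inferences are tempting and not supported:

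- That the sections contradict each other on a second sustained QTc above 500 ms. Section 5.1.3 is silent there; 5.1.2.3 is explicit.
- That the grade rows of Table 1 tell sites to continue at full dose after a rise above 60 ms. That borrows a grade label describing the Phase II study, and 5.1.3 sets QTc apart as needing special consideration.
- That change-only events go unrecorded. Under Section 5.2.1 an ECG deterioration that changes study treatment is an adverse event, so it is captured on the eCRF, though not necessarily within 24 hours.

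**Conclusion.** The inconsistency is real and should be corrected. In order of weight: the restart criteria differ, and the 5.1.3 value has no effect for a change-only interruption; the permanent stop is firmer in 5.1.2.3 than in 5.1.3; the reference is called both baseline and pretreatment, and the screening ECG may be an on-drug tracing; and the triggers differ at exactly 60 ms.

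The expected number of patients is small, about 1 in 132 for the restart problem and at most 3 in 132 for any 5.1.3 trigger. This assumes that the Phase II rates carry over. They may be lower here, because Section 4.1.2 excludes patients whose adverse event required discontinuation. None of the Phase II events was serious or led to dose modification or interruption. A reader might infer that the study's results are at risk, but Section 6 plans descriptive summaries only; no hypothesis test, sample size or planned analysis is affected.

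**What to change.** Replace the QTc text under Table 1 with the 5.1.2.3 rule, applied to all patients and not only those with metastatic melanoma:

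- Interrupt at QTc >500 ms or change ≥60 ms.
- Correct electrolytes and repeat the ECG weekly.
- Restart one dose level lower only after the QTc has normalized. Use one numeric definition in both sections, requiring at minimum both QTc <500 ms and change <60 ms. This is a floor: a patient with B = 400 interrupted at 460 would meet it at 459, so the clinical team should set the value and may well choose a stricter one.
- Treatment should be stopped permanently at QTc >500 ms with change >60 ms, and at a second sustained QTc >500 ms despite dose reduction.

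Use one reference term in both sections. Do not default to the rollover screening ECG: take the ECG before any vemurafenib from the antecedent study where available, otherwise the screening/baseline ECG.

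The cost is amendment wording and its routine approval under Section 9.5. No assessment is added beyond those in 5.1.2.3. When choosing a stricter restart value, the team should weigh that a longer hold may pass the 28-day limit.

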### **5.1.3 Dose Interruption/Modification for Adverse Events**

If a dose is missed, it can be taken 4 or more hours before the next dose to maintain the twice-daily regimen. Both doses should not be taken at the same time.

Management of symptomatic adverse drug reactions (e.g., arthralgia, fatigue, rash) may require either temporary interruption or dose reduction of vemurafenib treatment or both. When dose reduction is needed, dose reduction in 240-mg BID increments is recommended depending on individual safety and tolerability. Dose escalation after dose reduction is generally not recommended unless under special circumstances (i.e., increased likelihood of clinical benefit for the dose increase and no safety concerns). This should be done after discussion with the Sponsor. Dose increases above 960 mg BID will not be allowed.

For Grade 1 and tolerable Grade 2 toxicities, patients may continue with the full dose. For intolerable Grade 2 toxicities or Grade 3 toxicities, dosing will be interrupted until resolution to Grade 1 or lower and dose reductions in 240-mg increments are required. On the third appearance of intolerable Grade 2 or Grade 3 toxicity, despite two dose reductions, it is recommended that patients discontinue vemurafenib.

For Grade 4 toxicities, patients should discontinue study treatment or, on the basis of investigator judgment, study treatment should be interrupted until resolution to Grade 1 or lower with dose reduction of 50% upon restarting study drug. It is recommended that patients permanently discontinue vemurafenib for a second occurrence of any Grade 4 toxicities.

If treatment interruption has occurred for > 28 days for whatever reason, the patient will be considered to have permanently discontinued study treatment. Exceptions may be granted for reversible laboratory abnormalities with no clinical sequelae and/or clinical significance following consultation with the study's Medical Monitor. See [Table 1](#) below.

**Table 1 Dose Interruption/Modification Criteria for Vemurafenib; Regular Dose 960 mg BID**

Grade a	Recommended Dose Modification
Grade 1 or Grade 2 (tolerable)	Maintain vemurafenib at a dose of 960 mg BID
Grade 2 (intolerable) or Grade 3	
First appearance	Interrupt treatment until Grade 0–1. Resume dosing at 720 mg BID
Second appearance	Interrupt treatment until Grade 0–1. Resume dosing at 480 mg BID
Third appearance	Discontinue permanently
Grade 4	
First appearance	Discontinue permanently or interrupt vemurafenib treatment until Grade 0–1. Resume dosing at 480 mg BID
Second appearance	Discontinue permanently

BID=twice daily; NCI CTCAE=National Cancer Institute Common Terminology Criteria for Adverse Events.

a The intensity of clinical adverse events graded by the NCI CTCAE, Version 4.0.

Special consideration must be taken with any patient in the study who experiences an increase in QTc > 500 ms or change from baseline > 60 ms. If the QTc exceeds 500 ms or the change from baseline is > 60 ms on ECG, vemurafenib treatment should be temporarily interrupted. When the QTc decreases to < 500 ms, re-initiation of vemurafenib treatment may occur and the dose should be reduced by one dose level.

Permanent discontinuation of vemurafenib treatment is recommended if the QTc increase meets both criteria of > 500 ms and > 60 ms change from pretreatment.

Dose modifications or interruptions are not recommended for cuSCC or new primary melanoma adverse reactions (suspected lesion should be biopsied or resected and confirmed by pathology). Confirmed cuSCC or new primary melanoma should be completely resected and treated according local institutional standard of care.

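### Table 1's restart doses assume 960 mg BID: after a first Grade 4 event its 480 mg restart is a 33% cut for a patient on 720 mg and no cut for one on 480 mg, where the text says 50%

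*Combined protocol and SAP*

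**What the plan says.** Sections 3.4.1 and 4.3.2.1 let a patient start at 960, 720 or 480 mg BID, according to the last antecedent dose. All doses are made up of 240-mg tablets, which must not be chewed or crushed.

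Table 1 is captioned "Dose Interruption/Modification Criteria for Vemurafenib; Regular Dose 960 mg BID". Its rows are:

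- Grade 1 or tolerable Grade 2: "Maintain vemurafenib at a dose of 960 mg BID".
- Intolerable Grade 2 or Grade 3, first appearance: "Interrupt treatment until Grade 0–1. Resume dosing at 720 mg BID". The second appearance resumes at 480 mg BID, and the third is a permanent stop.
- Grade 4, first appearance: "Discontinue permanently or interrupt vemurafenib treatment until Grade 0–1. Resume dosing at 480 mg BID". The second is a permanent stop.

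The text of Section 5.1.3 is written in relative terms. For intolerable Grade 2 or Grade 3, "dosing will be interrupted until resolution to Grade 1 or lower and dose reductions in 240-mg increments are required". For Grade 4, if the investigator does not discontinue, "study treatment should be interrupted until resolution to Grade 1 or lower with dose reduction of 50% upon restarting study drug". It also discourages raising a dose once reduced, except where benefit is more likely, there is no safety concern and the Sponsor has been consulted.

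Two parts of Section 5.1.2.3 send sites to Table 1 without exempting reduced-dose patients. Gastrointestinal Toxicity requires strict adherence to it for diarrhea. Cardiac Toxicity wants the QTc to normalize "before therapy is reinstated at a reduced dose. Dose reduction should occur as described in" Table 1. The QTc text under the table says "re-initiation of vemurafenib treatment may occur and the dose should be reduced by one dose level".

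**The concern.** The table and the text should give the same dose for every patient the protocol admits. A patient below 960 mg BID has usually been reduced for tolerability, before entry or during this study. If such a patient has a new severe event, a site following the table may restart at the same dose, while a site following the text would go lower. Section 1.2.1.3 reports pharmacokinetics proportional to dose from 240 to 960 mg BID, so a gap in dose is a gap of about the same size in exposure. Patient safety is at stake, as is uniform handling across sites in a study whose secondary objective is to describe safety and tolerability.

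**Working it through.** **Inputs.** Possible doses at onset: 960, 720, 480 mg BID (Sections 3.4.1, 4.3.2.1; reductions under 5.1.3). Tablet: 240 mg, taken whole (4.3.2.1). Table 1 resume doses: 720 (first Grade 2/3), 480 (second Grade 2/3), 480 (first Grade 4). Text rules: a 240-mg reduction for Grade 2/3, a 50% reduction for Grade 4.

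**Step 1: the plan's own figure.** Cut = (dose at onset − Table 1 dose) / dose at onset. From 960: (960 − 480)/960 = 50%. Table and text agree.

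**Step 2: first Grade 4 event at each dose.**

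| Dose at onset (mg BID) | Table 1 restart | Cut under Table 1 | 50% cut under the text |
|---|---|---|---|
| 960 | 480 | 480/960 = 50% | 480 mg = 2 tablets |
| 720 | 480 | 240/720 = 33% | 360 mg = 1.5 tablets |
| 480 | 480 | 0/480 = 0% | 240 mg = 1 tablet |

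From 720 mg the table dose is 480/360 = 1.33 times the text dose, and the text dose cannot be given as whole tablets. From 480 mg the table gives no reduction. Neither result depends on how Grade 2/3 appearances are counted. Both apply whether the reduction came before entry or during this study.

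**Step 3: first intolerable Grade 2 or Grade 3 event, resume at 720.** Change = 720 − dose at onset.

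- From 960: −240 mg, as the text requires.
- From 720: 0. The text gives 720 − 240 = 480, so the table dose is 720/480 = 1.5 times the text dose.
- From 480: +240 mg. The daily dose goes from 2 × 480 = 960 mg to 2 × 720 = 1440 mg, up 50%, where the text calls for a reduction.

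**Step 4: when the Step 3 conflict arises.**

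- *Appearances counted from entry.* A 720 or 480 mg entrant meets the 720 row at the first event.
- *Antecedent events carried over, one step down per event.* A 720 mg entrant's next event is the second (resume 480 = 720 − 240) and a 480 mg entrant's is the third (stop). There is no conflict.
- *Either count, after a Grade 4 restart.* A patient on 960 mg with no earlier Grade 2/3 event is restarted at 480 after Grade 4, then has a first Grade 3 event. The 720 row applies, a 240-mg rise.

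The protocol does not say which count applies. Section 5.1.3 links the third appearance to two earlier reductions, which hints that reductions count. Section 4.5.2.2 carries antecedent cycles forward only to set the visit schedule. Carry-over would also remove the Grade 4 conflict for a patient who reached 480 mg through an antecedent Grade 4 event, since the next would be the second and therefore a stop.

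**Step 5: the other rows.** The second Grade 2/3 row is not a separate conflict: from 720, resuming at 480 is the required 240-mg step. The row that maintains 960 mg would, read literally, add 240 mg for a patient on 720 and 480 mg for one on 480, but no site would sensibly read it so; it is a wording point. QTc restarts already call for a lower dose. What is missing there is a level below 480 mg.

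**The case against.** The best defense is that the caption limits Table 1 to a patient on the regular 960 mg dose and that the relative rules in Section 5.1.3 cover everyone else. Several points support this. The table's column is headed as a recommendation, whereas the text makes the 240-mg reductions mandatory. Section 4.3.2.1 refers sites to Section 5.1 as a whole, not to the table alone. A patient just recovered from a Grade 3 event can hardly meet the no-safety-concern condition for escalation.

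Much of this stands for the Grade 2/3 row. A reader might infer that the protocol instructs sites to raise the dose of a 480 mg patient. The documents do not support that: only the literal table row does so, and the text beside it forbids it in substance. The exception is diarrhea, where the protocol demands strict adherence to Table 1.

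The defense does not remove the Grade 4 conflict. If the caption does exclude reduced patients, they have no table at all, and the text's 50% cannot be followed from 720 mg. If the 50% is read as half of the regular 960 mg, table and text agree, but a patient on 480 mg still restarts unreduced.

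It is also fair that a Grade 4 restart is optional, that permanent discontinuation is listed first, and that intolerance is a stopping ground in Section 4.5.3.1. These lower the risk, but the restart is still offered and needs a usable dose.

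**Conclusion.** The point holds and should be fixed. The main conflict is the first Grade 4 restart: a 33% cut from 720 mg and none from 480 mg, against a stated 50%. The Grade 2/3 conflict is secondary. It rests on counting appearances from entry, or on the sequence of a Grade 4 restart followed by a first Grade 3 event, and the text of Section 5.1.3 argues against acting on it.

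Two stronger readings should be avoided. Dividing the table dose by 240 mg BID would give 2-fold and 3-fold gaps for patients on 480 mg. The protocol never lists 240 mg BID as a treatment level and does not say whether a patient at 480 mg should step down or stop, so those ratios have no settled denominator. The supportable ratios are 1.33 for Grade 4 from 720 mg and, conditionally, 1.5 for Grade 2/3 from 720 mg. Section 5.1.1 says about half of earlier patients needed an interruption and/or a reduction. That figure pools the two and comes from other studies, so it does not show how many enter here below 960 mg; the number is not given.

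There is no hypothesis test and the analysis is descriptive, so no statistical result changes.

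**What to change.** Restate Table 1 relative to the dose at event onset:

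- **Grade 1 or tolerable Grade 2:** maintain the current dose.
- **Intolerable Grade 2 or Grade 3:** interrupt until Grade 0–1, then resume one 240-mg BID level lower (960 to 720, 720 to 480), never at or above the dose at onset. Third appearance: discontinue.
- **Grade 4, first:** discontinue, or restart at a whole-tablet dose below the dose at onset: 480 from 960, and from 720 a stated dose of either 480 (33% cut) or 240 (480/720 = 67% cut). Second: discontinue.
- **At 480 mg BID:** one stated action, either 240 mg BID or discontinuation, for Grade 2/3, Grade 4 and QTc restarts.

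In Section 5.1.3, refer to the current dose where the text now speaks of the full dose, and replace the 50% rule with a reference to the whole-tablet dose in Table 1. Add one sentence saying whether appearances and reductions in the antecedent study count.

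The documents do not settle three choices, so the clinical team must make them: the action at 480 mg, weighed against the continued-access objective; the Grade 4 dose from 720 mg; and the counting rule. The cost is one revised table and a few text edits at the next amendment, with no extra patients, visits or procedures.
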